### **Primary Performance Objective**

Objective: To demonstrate that percent time oxygen saturation is maintained in a target range is higher than standard practice. More specifically, to demonstrate that Vapotherm OAM used in conjunction with Vapotherm Precision Flow Hi-VNI is superior to standard practice for maintaining infants' arterial blood oxygen saturation in a target range, thus minimizing the proportion of time the subject is exposed to elevated or reduced levels of oxygen in the inspired gas.

Endpoint: The proportion of time (expressed as a percentage) spent in the targeted arterial blood oxygen saturation range. The percentage will be measured by pulse oximetry (SpO2), to determine the ability of the OAM to effectively titrate FiO2 to the needs of the infant. This value will be assessed by abstracting and analyzing recorded data over two contiguous randomized 24-hour study periods; one period with automated control (OAM) and one 24-hour period with manual control.

Subjects to Analyze: Subjects in the mITT cohort will be the primary analysis. Additional supplemental analyses will repeat this analysis using the FAS, the PP and Challenge cohorts. This will be used to provide an Adverse Event(s) summary.

#### Hypothesis:

Ho:  $D \leq 0$

Ha:  $D > 0$ ,

Where D = difference in proportion of time in range (OAM – standard practice)

# Vapotherm, Inc

## MODERATION Neo – Maintaining Optimal DEliveRy Using Automatic TItration of OxygeN Neonatal

Confidential

Analysis Method: The difference (OAM – standard practice) of the proportion of time in range will be tested using a paired t-test using a one-sided alpha of 0.025.

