# Vapotherm, Inc

## MODERATION Neo – Maintaining Optimal DEliveRy Using Automatic TItration of OxygeN Neonatal

**Confidential**

2. Patients that clinically require SpO2 maintenance within the target range of 90-95%
3. A need for supplemental oxygen as demonstrated by a required FiO2 > 0.25 at enrollment
4. Requiring a flow rate of greater than 2 L•min such that the assumed inspired oxygen fraction matched delivered oxygen fraction (definition of HVNI).
5. A minimum of 6 manual FiO2 adjustments in the 24hr period prior to trial enrollment.
6. Willing/Able to complete informed consent.

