### IV. Study Design

This study will be a prospective, multi-center, randomized, crossover trial of automated oxygen titration versus manual titration (conventional method). Patients enrolled will have their FiO2 managed by two mechanisms of titration (study arms) for two consecutive 24-hour periods in random order.

- Automated control (OAM), where the FiO2 is adjusted by the OAM system with clinical staff ability to override FiO2 when required, and instructed to do so – regardless of the mode
- Manual control (Manual), where FiO2 is only adjusted by the clinical staff

In both arms, the infants will be receiving high velocity nasal insufflation treatment using the Vapotherm Precision Flow Hi-VNI.

The study model does not change the nature of care that is provided by the clinical staff, and the clinical staff will be largely naive to the function of the OAM mode. Therefore, if the clinical staff see fit to change FiO2 during the Automated arm of the study they may override the module by changing the setting on the Precision Flow (without interacting with the OAM). Any manual override, and the justification for the override, will be noted on the subject's Case Report Form (CRF). SpO2 will continue to be monitored on the ICU patient monitors per standard of care.

In both study arms, data for FiO2, nasal cannula HVNI flowrate, gas temperature, SpO2 and pulse rate will be logged every 1 sec by the OAM, as well as being displayed / logged by the usual patient monitoring systems in each unit. Note that the OAM can log any manual adjustments during auto mode (overrides) as well as all data while in manual mode (Auto mode off). Offline computerized analysis will reduce the recorded data for both periods to assess time spent in the specified SpO2 range, time spent above and below the specified SpO2 range as well as other benchmark SpO2 values (see Data Collection and Statistical Analysis). Time spent below benchmark FiO2 values will be assessed (e.g., FiO2 at 21%, <25%). OAM data will be analyzed based on a modified intention-to-treat, whereby for any time the automated system is manually overridden in the 24-hour window, these outcomes data will be included into the analysis as well as the number of occurrences where manual manipulation is needed.

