# Vapotherm, Inc

## MODERATION Neo – Maintaining Optimal DEliveRy Using Automatic TItration of OxygeN Neonatal

Confidential

If both of the non-inferiority tests below reject the null and conclude non-inferiority is achieved, we will test for superiority.

Superiority, proportion of time above range:

Ho:  $D \geq 0$

Ha:  $D < 0$ ,

where D = difference in proportion of time above range (OAM – standard practice)

Superiority, proportion of time below range:

Ho:  $D \geq 0$

Ha:  $D < 0$ ,

where D = difference in proportion of time below range (OAM – standard practice)

Analysis Method: The difference (OAM – standard practice) of the proportion of time in range will be tested using a paired t-test using a one-sided alpha of 0.025 to test non-inferiority. If both are passed, testing for superiority will be performed again using a one-sided alpha of 0.025. Both superiority tests must be passed in order to claim superiority.

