### **Secondary Performance Objective 1**

Objective: To demonstrate that the percent time SpO2 is maintained in a target range is higher than standard practice for subjects in each of the weight category subgroups (1000g-2500g, 2501g-3500g).

Endpoint: The proportion of time (expressed as a percentage) spent in the targeted arterial blood oxygen saturation range. The percentage will be measured by pulse oximetry (SpO2), to determine the ability of the OAM to effectively titrate FiO2 to the needs of the infant. This value will be assessed by abstracting and analyzing recorded data over two contiguous randomized 24-hour study periods; one period with automated control (OAM) and one 24-hour period with manual control.

Subjects to Analyze: Subjects in the mITT cohort will be the primary analysis. Additional supplemental analyses will repeat this analysis using the FAS, the PP and Challenge cohorts. This will be used to provide an Adverse Event(s) summary.

Hypothesis:

Ho: D ≤ 0

Ha: D > 0,

Where D = difference in proportion of time in range (OAM – standard practice)

Analysis Method: The difference (OAM – standard practice) of the proportion of time in range will be tested using a paired t-test using a one-sided alpha of 0.025 for subjects in each category using a Hochberg adjustment to control alpha.

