### Hypothesis:

Ho:  $D \leq 0$

Ha:  $D > 0$ ,

Where D = difference in proportion of time in range (OAM – standard practice)

Analysis Method: The difference (OAM – standard practice) of the proportion of time in range will be tested using a paired t-test using a one-sided alpha of 0.025 for subjects in each skin pigmentation (light or dark) category using a Hochberg adjustment to control alpha. Skin pigmentation classification will be based upon assessing the subject's skin tone as specified in Section XIII. Additionally, summaries by individual classification of skin pigmentation will be provided by each level using descriptive statistics along with a 95% confidence interval.

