# Vapotherm, Inc

## MODERATION Neo – Maintaining Optimal DEliveRy Using Automatic TItration of OxygeN Neonatal

Confidential

$-15.0\% \pm 16.2\%$  and  $-12.6\% \pm 10.8\%$ , respectively. Using the largest standard deviation of 16%, again using PASS 14, a sample size of 38 will be adequate with at least 95% power for each test with a one-sided alpha of 0.025 to detect a difference as small as 10%. Both safety endpoints are powered at 95% ensure overall power is at least 90%.

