### VI. Study Procedures

Necessary staff at each center will be trained on the study objectives, including the target SpO2 ranges, alarm limits and operation of the OAM. Care of the infants is not altered, and clinical staff have the option of overriding the OAM to make manual adjustment to FiO2 as needed throughout the study. During the Manual arm of the study, staff will be instructed to adjust FiO2 as per normal protocol and to respond to SpO2 alarms (titrating FiO2 up or down) in a typical manner. Sites will be selected which are already familiar with clinical use of the HVNI therapy.

After informed consent is received and the infant is enrolled, the descriptive data will be completed on the CRF and the order of providing FiO2 control will be randomly assigned (i.e. OAM in Automated mode followed by manual mode, or vice versa). The baby will remain instrumented to provide standard clinical monitoring (including SpO2). A second pulse oximetry probe will be put in place to send an SpO2 signal to the OAM without interrupting the SpO2 signal used for the standard patient monitoring, and the placement of the OAM SpO2 probe will be confirmed to be in the right hand (for pre-ductal values) and that the signal is valid.

The patient file will be created in the OAM and the OAM configured in recording mode; the start time will be noted in the CRF. For the manual arm, the OAM will be set to record but the automatic control setting will be left in the OFF configuration. For the automated arm, again the module will be set to record, but the automatic control setting will be selected to the AUTO mode. When the nurses conduct their routine hourly charting of SpO2 and FiO2, they are to confirm that the SpO2 reading on the OAM matches that on the standard patient monitor and that the FiO2 reading on the OAM matches that displayed on the Precision Flow.

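### None of the five tested endpoints in this two-period crossover is analysed with a period term; adding one is cheap and protects the estimate if the orders end up unequal

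*Combined protocol and SAP*

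**What the plan says.** Section IV (Study Design) has each infant managed by both methods for "two consecutive 24-hour periods in random order". Section VI (Study Procedures) says only that the order of FiO2 "control will be randomly assigned (i.e. OAM in Automated mode followed by manual mode, or vice versa"); it gives no ratio, blocking or stratification of order.

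Section V gives the tests:

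- Primary Performance Objective: the difference "of the proportion of time in range will be tested using a paired t-test" at one-sided 0.025.
- Primary Safety Objective (time above and time below range, margin 5 points): "paired t-test using a one-sided alpha of 0.025 to test non-inferiority", then superiority at the same level.
- Secondary Performance Objective 1 (weight): "paired t-test using a one-sided alpha of 0.025 for subjects in each category using a Hochberg adjustment to control alpha".
- Secondary Performance Objective 2 (pigmentation): "paired t-test using a one-sided alpha of 0.025 for subjects in each skin pigmentation (light or dark) category", also with Hochberg.

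No period or sequence term appears anywhere. The Missing Data section defers only missing-data details to a separate SAP, so the crossover model is not promised elsewhere. The additional analyses are descriptive and outside this point.

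**The concern.** In a two-period crossover each infant's difference contains the treatment effect and, with a sign that depends on the order, any change between period 1 and period 2. A paired t-test removes that change only if the two orders are equally represented. Even then the change stays in the estimated variance.

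A period effect is plausible here. Infants qualify through at least six manual FiO2 "adjustments in the 24hr period prior to trial enrollment", so they enter on a labile day and may settle, or not, over the next 48 hours. The documents neither show nor size such an effect.

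Unequal orders are also plausible. No allocation method is stated, attrition of up to 15% is allowed for, and the mITT set keeps only infants with time on both treatments. Nor is order said to be balanced within the weight or pigmentation subgroups.

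Three results are exposed: safety non-inferiority if the true effect is near the 5-point margin, safety superiority at the 10-point alternative used for planning, and the subgroups of about 17 that are tested for labeling claims.

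**Working it through.** **1. The plan's sample sizes reproduce.** For an exact paired t-test at two-sided 0.05, equivalent to one-sided 0.025, dividing by 3/π for the nonparametric adjustment:

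- Primary (SD 11, difference 6, 90% power): 38; 38/(3/π) = 39.8, so 40, as stated.
- Safety (SD 16, difference 10, 95% power): 36; 37.7, so 38. The plan says "a sample size of 38 will be adequate with at least 95% power for each test".
- Subgroups (SD 16, difference 14, 90% power): 16; 16.8, so 17, as stated.

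The planned numbers are not in question.

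**2. Model.** Let D be the treatment difference (OAM − manual) and π_p the period shift (period 2 − period 1). An infant's OAM − manual difference has mean D − π_p if OAM came first (n1 infants) and D + π_p if manual came first (n2 infants).

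- Conditional bias of the paired mean: π_p × (n2 − n1)/N.
- Period-adjusted estimate: the average of the two order means. It has no period bias; SE = (SD/2) × √(1/n1 + 1/n2), N − 2 df.

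**3. Bias.** The documents give no π_p, so 2 and 5 points are assumed.

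- N = 40, split 24:16: 2 × 8/40 = 0.4; 5 × 8/40 = 1.0 points.
- n = 17, split 11:6: 2 × 5/17 = 0.6; 5 × 5/17 = 1.5 points.

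**4. How often.** If order is assigned by simple randomisation (an assumption), 24:16 or worse has probability 0.268 (0.134 in each direction), and 11:6 or worse among 17 has probability 0.332 (0.166 in each direction).

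**5. Error rates.** Simulated with at least 400,000 trials per cell, one-sided 0.025, shift 2 to 5 points. The pilot SDs (10.8 and 16.2 from Table 1; 16 for subgroups) come from an order-randomised crossover and may already contain period variance. Each was therefore taken once as the within-order SD and once as the total SD; the ranges cover both readings.

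| Quantity | Split | Paired t-test | With period term |
|---|---|---|---|
| Non-inferiority type I error at D = 5, SD 10.8 | 24:16 favouring OAM | 0.039–0.060 | 0.024–0.026 |
| Same, SD 16.2 | 24:16 favouring OAM | 0.034–0.049 | 0.024–0.026 |
| Same, either SD | 24:16 against OAM | 0.002–0.017 | 0.024–0.026 |
| Same, either SD | 20:20 | 0.014–0.025 | 0.024–0.026 |
| Safety superiority power at −10, SD 16.2 | 24:16 against OAM | 0.915–0.956 | 0.961–0.974 |
| Same | 24:16 favouring OAM | 0.977–0.990 | 0.961–0.974 |
| Subgroup type I error per test (before Hochberg), SD 16 | 11:6 favouring OAM | 0.033–0.047 | 0.024–0.026 |
| Same | 11:6 against OAM | 0.008–0.017 | 0.024–0.026 |
| Subgroup power at 14 | 11:6 against OAM | 0.835–0.90 | 0.90–0.92 |

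With no period effect, the paired powers are 0.97 (superiority) and 0.92 (subgroup). Averaged over simple-randomisation splits, paired type I error is 0.025.

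**6. Equal orders.** The estimate and its true sampling variance do not change; the reported SE does. For N = 40, within-order SD 11 and a shift of 5, the paired SD becomes √(121 + 4 × 25 × 20 × 20/(40 × 39)) = √146.6 = 12.1, so the SE is 1.92 instead of 11/√40 = 1.74.

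**7. At the planned effects.** With true safety differences of −12.6 and −15.0, non-inferiority power is 1.00 in every cell, with or without the term.

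**The case against.** The strongest reply is that the planned test is valid. Order is randomised, so over repeated allocations the paired test is unbiased with error 0.025, and with equal orders it is conservative. That is correct, and the bias described here is conditional on the realised split. But only one split will be realised, and the estimate and interval are read at that split.

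Next, harm needs several things together: a period shift, an uneven split in the harmful direction, and a true effect near a boundary. The shift is assumed, six adjustments in 24 hours is only a minimum threshold, and 24-hour arms were chosen to cover diurnal variation. Blocked allocation would remove most of the imbalance. All of this limits the weight of the point. It does not remove it: covering time of day does not exclude drift from the first day to the second, and blocking the trial as a whole does not balance dropouts or subgroups.

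The pilot differences (28.4, −15.0, −12.6) are also far from any boundary. That stands. So does the remark that equal orders cost reported rather than true precision, and that a split favouring OAM raises paired power.

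Finally, the term is less cheap in small, uneven subgroups. With no period effect, subgroup power at 14 points falls from 0.92 to 0.87 at 12:5 and to 0.82 at 13:4; 12:5 or worse occurs about 14% of the time under simple randomisation. This is a real cost and should be accepted knowingly.

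**Conclusion.** The concern holds, as a recommended improvement and not as a flaw that invalidates the trial. The five tested endpoints are analysed without the factor the design randomises. Under an assumed shift of 2 to 5 points and a 24:16 split, the reported safety difference is off by 0.4 to 1.0 points, up to a fifth of the 5-point margin, and the error at that margin can reach 0.06 or fall to 0.002. Safety superiority power can fall below the planned 95%, and subgroup power below the planned 90%. The result rests on the assumed shift and on the realised split; averaged over allocations there is no bias, and at the planned effects no conclusion is likely to change. Confidence is medium because the documents do not give the size of any period effect.

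**What to change.** For the two safety endpoints, the primary performance endpoint and both secondary endpoints, make the standard 2x2 crossover analysis primary. Suggested wording: *The treatment difference (OAM − manual) will be estimated from a linear mixed model with fixed effects for treatment, period and sequence and a random infant effect; D will be tested against the stated null values at one-sided 0.025.*

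State the degrees-of-freedom method. The mITT set requires time on both treatments; for complete pairs the model equals a comparison of within-infant period differences between the two orders, with N − 2 df, and could be specified in that simpler form. Fit it within each subgroup for the secondary endpoints. Leave margins, alpha, Hochberg and sample size unchanged. Report results by order, keep the paired t-test as a sensitivity analysis, and state how order is allocated. Settle this before outcome data are seen, so that the adjustment does not look post hoc.

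The cost is SAP wording, a few lines of code and one degree of freedom (primary power 91.98% to 91.94% at 20:20 with no period effect). If there is no period effect and the orders are unequal, the SE widens:

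- N = 40, SD 10.8, 24:16: from 10.8/√40 = 1.71 to 5.4 × √(1/24 + 1/16) = 1.74, about 2%.
- n = 17, SD 16, 11:6: from 16/√17 = 3.88 to 8 × √(1/11 + 1/6) = 4.06, about 5%; power at 14 points goes from 0.92 to 0.90, and lower at more extreme splits.

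A period term does not address carryover between the contiguous periods.

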### **Secondary Performance Objective 1**

Objective: To demonstrate that the percent time SpO2 is maintained in a target range is higher than standard practice for subjects in each of the weight category subgroups (1000g-2500g, 2501g-3500g).

Endpoint: The proportion of time (expressed as a percentage) spent in the targeted arterial blood oxygen saturation range. The percentage will be measured by pulse oximetry (SpO2), to determine the ability of the OAM to effectively titrate FiO2 to the needs of the infant. This value will be assessed by abstracting and analyzing recorded data over two contiguous randomized 24-hour study periods; one period with automated control (OAM) and one 24-hour period with manual control.

Subjects to Analyze: Subjects in the mITT cohort will be the primary analysis. Additional supplemental analyses will repeat this analysis using the FAS, the PP and Challenge cohorts. This will be used to provide an Adverse Event(s) summary.

Hypothesis:

Ho: D ≤ 0

Ha: D > 0,

Where D = difference in proportion of time in range (OAM – standard practice)

Analysis Method: The difference (OAM – standard practice) of the proportion of time in range will be tested using a paired t-test using a one-sided alpha of 0.025 for subjects in each category using a Hochberg adjustment to control alpha.

### **Secondary Performance Objective 2**

Objective: To demonstrate that the percent time SpO2 is maintained in a target range is higher than standard practice for subjects with both light and dark skin pigmentation.

Endpoint: The proportion of time (expressed as a percentage) spent in the targeted arterial blood oxygen saturation range. The percentage will be measured by pulse oximetry (SpO2), to determine the ability of the OAM to effectively titrate FiO2 to the needs of the infant. This value will be assessed by abstracting and analyzing recorded data over two contiguous randomized 24-hour study periods; one period with automated control (OAM) and one 24-hour period with manual control.

Subjects to Analyze: Subjects in the mITT cohort will be the primary analysis. Additional supplemental analyses will repeat this analysis using the FAS, the PP and Challenge cohorts. This will be used to provide an Adverse Event(s) summary.

# Vapotherm, Inc

## MODERATION Neo – Maintaining Optimal DEliveRy Using Automatic TItration of OxygeN Neonatal

Confidential

### Hypothesis:

Ho:  $D \leq 0$

Ha:  $D > 0$ ,

Where D = difference in proportion of time in range (OAM – standard practice)

Analysis Method: The difference (OAM – standard practice) of the proportion of time in range will be tested using a paired t-test using a one-sided alpha of 0.025 for subjects in each skin pigmentation (light or dark) category using a Hochberg adjustment to control alpha. Skin pigmentation classification will be based upon assessing the subject's skin tone as specified in Section XIII. Additionally, summaries by individual classification of skin pigmentation will be provided by each level using descriptive statistics along with a 95% confidence interval.

## **Additional Analyses**

These exploratory analyses will use descriptive statistics to quantify values in each arm and the difference (OAM – standard practice). These analyses will use the mITT and PP populations except for adverse event summaries

To quantify and compare OAM automatic mode to standard manual practice performance with additional measures including:

- Proportion of Time, Number of Episodes, and Average Duration of Episodes in both high and low SpO2 ranges (with or without FiO2 at or above 21%)
  - SpO2 below target range
  - SpO2 below 80% for episodes  $\geq 60$ s
  - SpO2 below 80%
  - SpO2 above target range at FiO2>0.21 (not at air)
  - SpO2 below 70%
  - SpO2 in 80% to 86% range
  - SpO2 in target range at FiO2=0.21
  - SpO2 above 98% at FiO2>0.21 (not at air)
  - SpO2 below target range at FiO2=0.21
- Number of manual adjustments to FiO2 in manual mode compared to automated control (manual override).
- Proportion of Time at or below FiO2 ranges compared between study arms
  - FiO2 at 0.21 (air)
  - FiO2 below 0.25
- SpO2 fluctuations compared to manual control
  - Coefficient of variance for SpO2 for the study arm
  - Standard deviation of SpO2 for the study arm

